## **9.5 Halting Rules**

If an UP develops that is a significant threat to the safety of participants, or if the number of SAEs overall or the number of occurrences of a particular type of SAE raises concerns, the NIDCR may temporarily suspend enrollment until a safety review is convened. The objective of such a review would be to decide whether the study should continue per protocol, proceed with caution, be further investigated, be modified and then continued, or be discontinued.

## **10. STUDY OVERSIGHT**

In addition to the PIs' responsibility for oversight, study oversight will be under the direction of a Data and Safety Monitoring Board (DSMB) appointed by the NIDCR. The DSMB will operate under the rules of an NIDCR-approved charter that will be approved at the organizational meeting of the DSMB. The conduct of the DSMB and rules regarding how often the Board will meet will be defined by the DSMB charter for the study. At this time, most data elements that the DSMB needs to assess will be clearly defined. It is anticipated that the DSMB will meet at least once per year via teleconference to assess safety and efficacy data, study progress, and data integrity for the study. If safety concerns arise, more frequent meetings may be held. The DSMB will provide recommendations to the NIDCR.

## **11. CLINICAL SITE MONITORING**

Clinical site monitoring is conducted to ensure that the rights of human subjects are protected, that the study is implemented in accordance with the protocol and/or other operating procedures, and that the quality and integrity of study data and data collection methods are maintained. Monitoring for this study will be performed by NIDCR's Clinical Research Operations and Management Support (CROMS) contractor. The monitor will evaluate study processes and documentation based on NIDCR standards and the International Council for Harmonisation (ICH), E6: Good Clinical Practice (GCP) guidelines.

Details of clinical site monitoring will be documented in a Clinical Monitoring Plan (CMP) developed by the CROMS contractor, in collaboration with the NIDCR Office of Clinical Trials and Operations Management (OCTOM) and the NIDCR Program Official. The CMP will specify the frequency of monitoring, monitoring procedures, the level of clinical site monitoring activities (e.g., the percentage of subject data to be reviewed), and the distribution of monitoring reports. Some monitoring activities may be performed

remotely, while others will take place at the study site(s). Staff from the CROMS contractor will conduct monitoring activities and provide reports of the findings and associated action items in accordance with the details described in the CMP. Documentation of monitoring activities and findings will be provided to the site study team, the study PIs, OCTOM, and the NIDCR. The NIDCR reserves the right to conduct independent audits as necessary.

Monitoring visits will include, but are not limited to: review of site assessment and staff training; human subjects protection; protocol compliance; regulatory compliance; laboratory SOPs and compliance; laboratory sample disposition, storage, and handling; quality assurance; adverse event reporting; and integrity of research data and samples.

## **12. STATISTICAL CONSIDERATIONS**

### **12.1 Study Hypotheses**

**Primary Hypothesis 1:** Women in CP groups that include the CPOP intervention as part of their CP prenatal care will have significantly greater improvement in clinical OH and hygiene outcomes during pregnancy (reduced % sites bleeding on probing (BOP), reduced % sites with probing depths  $\geq 4$ mm (PD4), reduced Plaque Index (PI) scores compared to women receiving CP usual care.

**Primary Hypothesis 2:** Infants of mothers in CP groups that include the CPOP intervention as part of their CP prenatal care will be significantly less likely to have the presence of salivary MS at age 12 months, compared to infants of mothers receiving CP usual care.

**Secondary Hypothesis 1:** Women in CP groups that include the CPOP intervention as part of their CP prenatal care, compared to women receiving CP usual care will have significantly greater increases in:

- A. Maternal OH knowledge, attitudes, and hygiene behaviors during pregnancy;
- B. Maternal infant-related OH knowledge and attitudes during pregnancy at 12 months postpartum; and
- C. Maternal OH practices with their infant at 12 months postpartum.

**Secondary Hypothesis 2:** Infants of mothers in CP groups that include the CPOP intervention as part of their CP prenatal care will be significantly less likely to have the presence of salivary LB at age 12 months, compared to infants of mothers receiving CP usual care.

**Secondary Hypothesis 3:** Maternal OH knowledge, attitudes, and/or behaviors will result in significant mediation of the relationships between intervention arm and maternal OH (plaque levels, BOP and PD4) and infant OH risk (salivary bacteria incidence) outcomes.

## 12.2 Sample Size Considerations

**Sample size estimate and power analyses.** We assume 80% power; two-tailed  $\alpha=0.05$ ; 75% retention at 12 months; binary outcomes describing maternal gingival 1) pocket depth  $\geq 4$ mm (PD4) and 2) bleeding on probing (BOP) at each probed site (max=168; in pilot data  $\bar{x}=159$  sites per participant); 3) a continuously coded maternal plaque index score (PI: range 0-4); and 4) a child-level binary MS colonization indicator. The PD4 and BOP data for mothers will have a 5-level nested structure with a) 5 CP sites, b) 2-5 CP facilitators per CP site for a total of 14 CP facilitators participating in the study, c) 3-4 CP groups per facilitator for a total of 49 CP groups with participants enrolled in the study, and, on average, e) 8 study-enrolled mother-child dyads per CP group, and f) 159 gingival probe sites per mother; the maternal PI data and the child-level MS data will share the first four levels. The total sample size estimate is 392 mother-child dyads (49 CP groups  $\times$  8 mother-child dyads/CP group results in a total of 392 month-child dyads). Power analyses assumed two randomized groups including 8 and 6 CP facilitators, respectively. From our pilot data, we estimated intra-cluster correlations (ICC) for maternal PD4 equal to 0.001 for CP sites, facilitators, and groups, as well as 0.13 for CP women; ICCs for BOP equaled 0.04 for CP sites, facilitators, and groups, as well as 0.27 for CP women; ICCs for maternal PI equaled 0.13 for sites and 0.14 for facilitators and groups; ICCs for the child MS outcome equaled 0.01 for CP sites and CP facilitators as well as 0.04 for CP groups.

	observed effect in pilot	min. detectable effect
BOP: Ctrl v Intv (mothers)	16.7% v 10.7% OR=1.67, power>0.97	16.7% v 11.8% OR=1.50, power=0.80
PD $\geq 4$ mm: Ctrl v Intv (mothers)	20.4% v 17.0%* OR=1.25, power=0.80	20.4% v 17.0%* OR=1.25, power=0.80
PI (means) Ctrl v Intv (mothers)	0.95 v 0.76 d=0.41, power=0.89	0.95 vs 0.78 d=0.37, power=0.80
MS: Ctrl v Intv (children)	24.9% v 6.5% OR=4.77, power=0.97	24.9% v 10.9% OR=2.71, power=0.80

\* observed and minimum detectable effects equivalent w/in rounding;  
d represents a group difference of standardized means

We present power to detect the effect sizes observed in our pilot study as well as the minimum detectable effects with 80% power. We note that although the observed effect on MS (OR=4.77) is considered 'large,' two reasons to choose the proposed design are that it,

conservatively, is capable of detecting a 'medium' sized effect on MS (OR=2.71) and, more importantly, it is capable of detecting the smaller effect sizes anticipated on maternal outcomes. For the mediation test to help explicate mechanisms of action we further assumed a correlation of 0.30 between experimental groups and a unit-standardized continuous mediator describing maternal OH behavior: the minimum detectable indirect effect of experimental groups on the binary child MS indicator corresponded to an OR=1.30^33. Power was calculated by simulation via multilevel logistic models with Laplace estimation; the simulations also suggested that for the proposed experimental design, the modeling framework produces unbiased parameter and standard error estimates.

## 12.3 Planned Interim Analyses (if applicable)

No planned interim analyses.

## 12.4 Final Analysis Plan

Proposed statistical analyses: Descriptive analyses will estimate means and proportions, measures of variability, and confidence intervals (CIs). We will determine whether participant baseline characteristics are independent of intervention group assignment (randomization check) and attrition (attrition analysis).

Missing data. Case-wise deletion of missing data will not be used for analysis because it relies on the relatively strong *missing completely at random* assumption and entails a loss of statistical power. Instead, multiple imputation will allow models to be fit to all available data and will invoke the relatively mild assumption that the data are *missing at random*, conditional on modeled variables.

Primary Analyses will include intention-to-treat comparisons. The multilevel data structure will be accommodated by generalized linear mixed models (GLMMs) with random intercepts for CP centers, facilitators, groups, mothers/children, and repeated assessments (for maternal outcomes; PROC GLIMMIX). Main outcomes include binomial indicators of mothers' BOP (# sites bled/# sites probed) and PD4 (# sites with  $\geq 4$ mm pocket depth/# sites probed,) continuous indicator of maternal plaque levels, and a binary outcome of child oral MS colonization (multilevel logistic regression via Laplace estimation); and a count of child MS colonization (multilevel zero-inflated Poisson or a zero-inflated negative-binomial model, as appropriate, via Laplace). Each maternal outcome will be regressed onto indicators of experimental groups and assessment time, as well as the group-by-time interaction. Child MS outcomes at 12-months will be regressed onto the experimental group indicator. Significant intervention group main effects at follow-up and group-by-time interaction effects will be interpreted and described. If any key demographic or risk factors are imbalanced at baseline, we will include a quintile-stratified propensity adjustment, which can significantly reduce bias. Propensity scores will be estimated by regressing the intervention group indicator onto baseline characteristics of participants (averaged up to the unit of randomization); covariate balance across groups will be assessed. Next, propensity score quintiles will be formed. Regression models will initially include a quintile-by-groups-by-time interaction term to test whether the intervention effect is equivalent across quintiles. A significant interaction term would suggest quintile-specific treatment effects, which would then be estimated and reported. If the interaction term is non-significant, then it would be removed and the intervention effect estimated, conditional on the propensity-quintile main effect.

Secondary analyses will include multilevel linear models of secondary outcomes: OH knowledge, self-efficacy, importance, behavior scores; and multilevel binary and zero-inflated count outcome models of child LB and TVC levels. Additional multilevel models will explore whether any intervention effects are moderated by maternal race/ethnicity,

language, socioeconomic status, CP site, and baseline maternal OH knowledge and behaviors.

Mediation analyses to help assess mechanisms of action: We will test whether experimental group assignment impacts subsequent hypothesized maternal OH behavior mediators measured at the mid-study assessment period, as well as whether indirect effects of intervention groups on child MS outcomes via the candidate mediators are significant. Mediation will be tested with a series of linear, binary, and zero-inflated multilevel models, as appropriate, using methodological extensions to accommodate binary mediators and outcomes. A draft interim analysis plan will be developed in case the U01's DSMB requires interim analyses; an alpha-spending function with O'Brien-Fleming rule will be proposed to control Type I error.

Descriptive analyses of facilitator perceived feasibility and acceptability of the CPOP intervention within CP clinics and group sessions: When study activities have been completed in the CP sites, Intervention facilitators will complete acceptability and feasibility assessments. The purpose of these is to provide evaluation of the perceived impact of the CPOP interventions integrated into CP sessions in terms of value to CP moms, value to the CP programs, and burdens/challenges (time constraints, adjusting topic schedules) versus benefits in CP groups.

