## PROTOCOL SUMMARY

**Title:** CenteringPregnancy Oral Health Promotion (CPOP) Clinical Trial

**Précis:** A five-year, Phase III, multi-site, cluster randomized controlled clinical trial will evaluate the efficacy of the CenteringPregnancy (CP) Oral Health Promotion (CPOP) intervention. Intervention and control groups will be drawn from 5 CP sites. Prenatal care facilitators will conduct the intervention in group prenatal care sessions. With 2-5 CP facilitators per site (14 facilitators), conducting 3-4 CP groups each (49 CP groups with 8 mother/child dyads per group), the total study population will be approximately 392 mother-child dyads. CP facilitators will be randomly assigned to either the: 1) intervention arm and deliver the CPOP intervention; or 2) control arm and deliver the usual CP curriculum. The CPOP intervention consists of two 15-minute modules: 1) maternal oral health (OH) and 2) infant OH. The data collection will continue through 12 months postpartum. For the maternal OH module, pre- and post-intervention dental exams of gingival OH and Plaque Levels, and knowledge, attitudes and behavior (KAB) questionnaires during the prenatal period will be used to assess maternal OH outcomes. For the infant OH module, pre and post-module KAB questionnaires will be completed during the prenatal period. Infant OH risk status – the presence of caries-causing bacteria (*mutans streptococci* and *Lactobacilli*) in saliva of both mother and infant will be assessed when the infant is 12 months of age to determine differences in study arms. Analyses will include generalized linear mixed model regressions testing a treatment by time interaction to determine the significance of differences between intervention arms from pre-to post- intervention on the outcome variables. Additional analyses (Secondary Aim 2) will test mediation effects of knowledge, attitudes, and behaviors on relationships between treatment arm and primary study outcomes.

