## **4. STUDY DESIGN**

*Overview of Research Design.* We will conduct a cluster randomized controlled clinical trial to evaluate the efficacy of the CPOP intervention within the CP prenatal care group environment. The intervention will take place during the prenatal period and participants

will be assessed pre-intervention and post-intervention while still pregnant and followed through the first year postpartum to evaluate infant and maternal outcomes.

***Intervention Setting.*** The study will take place at 5 healthcare facilities that offer CP in the San Francisco Bay Area, most of which are community-based. The initiation of study activities in sites will be staggered in three waves approximately nine months apart, with two sites starting in each wave. CP groups at these 5 sites are conducted in either English or Spanish. We will recruit a minimum of 2-5 CP facilitators at each site to serve as either intervention or control facilitators. Facilitators will be randomized to one of two groups: 1) Intervention or 2) Control. Intervention facilitators will be trained in the intervention, which will include the facilitators practicing the Intervention delivery in a group of non-study CP moms. When study groups are initiated, the facilitators will conduct the interventions in approximately 3-4 cycles of prenatal groups. In each cycle, intervention facilitator will integrate the 2 intervention modules into 2 of their 10 CP group sessions. Control facilitators will not be trained and will not present the intervention modules within their CP groups. The control groups will receive the usual care CP curriculum. CP groups consist of 8-12 pregnant women of a similar gestational phase.

***CP Facilitators.*** We have identified a Site Champion at each CP site, an individual with influence and connection to the clinical and administrative leadership at the health care facility. Study staff will work with these Site Champions to present an overview of the study to the facilitators and to ask them to enroll in the study. They will be assured that they are free to participate or not, however, they will be aware that their site had made a group decision to participate. The facilitators will be randomized into the Intervention or the Control arm of the study. This means that all of the pregnant women enrolled in a particular facilitator's assigned CPOP study groups will either be Intervention or Control participants.

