#### ***5.4.1 Randomization Procedures***

CP Facilitators will be randomly assigned to either Intervention or Control arm according to a matched, restricted randomization plan. Intervention facilitators will receive CPOP training after assignment. Our primary concern is strengthening the basis for causal inference by establishing equivalent experimental groups at baseline. Randomizing 5 sites is not optimal and randomizing CP participants is not possible because the intervention is delivered to CP groups. Therefore, we have chosen to randomize 14 CP facilitators, using "restricted randomization" to ensure an acceptable level of balance across experimental groups at baseline (e.g., create two sets of CP facilitators balanced on preexisting variables describing relevant characteristics of CP sites, facilitators, and their served populations; then, randomize one set of CP facilitators to deliver CPOP and

the other to deliver usual care). Prior to randomization we will identify facilitators from our five clinical sites who agree to accept assignment as an Intervention or a Control facilitator. Once identified, we will collect descriptive data characterizing each participating CP site and facilitator, as well as the populations they serve; these data will be included in the restricted randomization process. Intervention facilitators will receive CPOP training approximately 2 months before site initiation.

Originally, we planned to randomize CP facilitators into two sets of equal size (i.e., 7 CP facilitators assigned to each set). However, with summary data in hand, preliminary restricted randomization solutions with equal set size failed to establish reasonable cross-set balance on variable describing characteristics of CP sites, facilitators, and their served populations. Next, we allowed for set sizes of with 8 and 6 CP facilitators, respectively. Allowing for an '8/6' split resulted in several restricted randomization solutions that balanced CP site, facilitator, and patient population characteristics within close tolerances. Therefore, we opted to randomize CP facilitators into two groups with one group including 8 CP facilitators and the other including 6 CP facilitators. Once a final '8/6' split was chosen, the study statistician flipped a coin to assign the two sets to CPOP Intervention versus usual care control.

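### The maternal group-by-time test is fitted with random intercepts only, so it has no facilitator-level error term, and section 12.4 does not say that this contrast decides Primary Aim 1

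*Combined protocol and SAP*

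**What the plan says.** - **Unit of randomisation** (section 5.4.1): "we have chosen to randomize 14 CP facilitators", split 8 and 6.
- **Test named** (Protocol Summary): "generalized linear mixed model regressions testing a treatment by time interaction to determine the significance of differences between intervention arms". The aim is worded to match in the Protocol Summary objectives and in sections 3.1.1 and 12.1, as greater improvement than usual care. Section 3.1.1 compares the post-intervention exam with baseline.
- **Fixed effects** (section 12.4): "Each maternal outcome will be regressed onto indicators of experimental groups and assessment time, as well as the group-by-time interaction".
- **Random effects** (section 12.4): "random intercepts for CP centers, facilitators, groups, mothers/children, and repeated assessments (for maternal outcomes; PROC GLIMMIX". No facilitator-by-time or CP-group-by-time term, robust variance or degrees-of-freedom rule is stated.
- **Interpretation** (section 12.4): "Significant intervention group main effects at follow-up and group-by-time interaction effects will be interpreted and described". Neither contrast is ranked above the other for Primary Aim 1.
- **Power** (section 12.2): rows such as "BOP: Ctrl v Intv (mothers)" show one control and one intervention value, with no pre-post correlation. The text says that simulation suggested unbiased standard errors, but it does not describe how change was generated.

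**The concern.** In a cluster trial the error term for the deciding contrast should include variation between the randomised units. The planned model contains a facilitator intercept, and that protects a comparison of arms at follow-up. It does not protect a comparison of change, because a constant intercept drops out of a before-after difference. If women's change varies between facilitators, the interaction's interval is too narrow and a false claim on Primary Aim 1 is more likely than 5%.

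The documents leave room for such variation without measuring it. Fidelity is scored as a proportion of learning objectives covered (section 8.1), so delivery can differ between intervention facilitators. That route exists in one arm only: "Control facilitators will not be trained and will not present the intervention modules within their CP groups". Usual-care oral health content is also described as inconsistent (section 2.2), which could matter in both arms. The unranked follow-up effect adds to the problem, because one contrast carries the clustering and the other does not.

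**Working it through.** **1. The plan's own figures.** 49 x 8 = 392 dyads, and 392/14 = 28 women per facilitator, so about 224 and 168 women per arm. Odds ratios: BOP (0.167/0.833)/(0.118/0.882) = 1.50; PD4 (0.204/0.796)/(0.170/0.830) = 1.25. Both agree with section 12.2.

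Plaque power was checked as a single-time arm difference. Section 12.2 says "ICCs for maternal PI equaled 0.13 for sites and 0.14 for facilitators and groups". Read cumulatively, that is 0.14 - 0.13 = 0.01 for facilitators beyond site, nothing further for groups, and 0.86 for women. With 75% retained and site cancelling:

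variance = 0.01(1/8 + 1/6) + 0.86(1/168 + 1/126) = 0.00292 + 0.01194 = 0.01486, SE = 0.122.

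The noncentral t on 12 df gives power 0.795 at d = 0.37 and 0.870 at d = 0.41, against 0.80 and 0.89 stated. The stated powers for the other outcomes do not all reproduce under one convention. They were simulated and the details are not given, so this shows no error, but it also does not show which contrast was powered.

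**2. What enters the interaction.** For plaque, write a record as fixed effects + site + facilitator + group + woman + residual. The first four random terms are identical at both exams. On its natural reading, the repeated-assessment intercept sits within the woman and acts as residual. Hence:

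SE(arm x time) = sqrt[2 x residual variance x (1/224 + 1/168)].

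With an assumed residual variance of 0.4, this is sqrt(0.8 x 0.010417) = 0.0913. A generalised least squares check (14 facilitators, 49 groups, 392 women; assumed woman variance 0.4, group variance 0.02) gives:

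| Facilitator intercept variance | SE, interaction | SE, follow-up difference |
|---|---|---|
| 0 | 0.0913 | 0.100 |
| 0.04 | 0.0913 | 0.148 |
| 0.14 | 0.0913 | 0.226 |
| 1 | 0.0913 | 0.549 |

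Direct REML fits of the two-record model agree. The mean reported interaction SE was 0.102, 0.103 and 0.102 when the share of change variance between facilitators was 0, 0.02 and 0.05. The true SD was 0.102, 0.127 and 0.158.

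**3. Type I error.** Let r be the share of the variance of change that lies between facilitators. It is an assumption, because the documents give none. With 28 women per facilitator, D = 1 + 27r and the error rate is 2[1 - Phi(1.96/sqrt D)]. At r = 0.01, D = 1.27 and the rate is 8.2%. At r = 0.02, D = 1.54 and the rate is 11.4%.

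If only the intervention arm (n_I women, against n_C controls) varies, D = [(1 + 27r)/n_I + 1/n_C]/(1/n_I + 1/n_C). At r = 0.02 this is 1.23 with 8 intervention facilitators (7.7%) and 1.31 with 6 (8.7%).

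Simulated rates for 392 women, over several independent runs:

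| r | Both arms vary | Intervention arm only | CP groups only |
|---|---|---|---|
| 0 | 4.7-5.2% | about 5% | about 5% |
| 0.01 | 7.9-8.4% | about 6-7% | 5.8% |
| 0.02 | 11.0-11.9% | about 8-9.5% | 6.4% |

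With 392 x 0.75 = 294 women, the both-arm rates are 5.1%, 7.4% and 10.0%. The 75% is the 12-month figure; section 12.2 gives none for the second dental exam. A small binomial check with the planned intercepts (250 runs, about +/-4 points) gave 3.2% at r = 0 and 14.4% at r = 0.02.

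**4. Link to the stated ICCs.**
- *Plaque:* r = 0.01 x (1 - a)/(1 - 0.5), with assumed cluster autocorrelation a of 0.8 to 0.9 and assumed within-woman correlation 0.5, gives r = 0.004 to 0.002. Type I error is then 5.8-6.3% if both arms vary and 5.1-5.7% if only the intervention arm does.
- *PD4:* the stated 0.001 leaves little room for inflation.
- *BOP:* not mapped. Its ICC is per probed site, and 0.04 at every level could mean no facilitator variance beyond site.

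**5. The alternative tests.** With both arms varying, the equal-variance t-test on facilitator means holds 4.8-5.3%. If only the intervention arm varies (r = 0.01 to 0.05), it rejects 4.1-4.5% when that arm has 8 facilitators and 5.2-6.7% when it has 6; Welch's version stays at 4.6-5.1%. A mixed model of change with facilitator and group effects and 12 df rejects 2.1-2.6% at r = 0.

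**The case against.** **The contrast is already named.** A reader might infer from section 12.4 that the plan leaves the deciding contrast for Primary Aim 1 open. The documents do not support that: the Protocol Summary names the interaction and the aim's wording fits it. The interpretation sentence can also be read respectively, with main effects for the child outcome and interactions for the mothers. What remains is that section 12.4 does not say so.

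**The model does include facilitators.** A reader might infer that clustering is ignored throughout. It is not. The facilitator intercept enters the follow-up difference, so the point concerns the interaction only.

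**The plan reports unbiased standard errors.** Section 12.2 does, from simulation. It does not say that the simulated data let change vary between facilitators. Data generated with intercepts alone could not reveal this problem, so the statement does not settle it.

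**Inflation is assumed, not shown.** This stands. At r = 0 there is none, and the part tied to stated ICCs is small. Common training, audio-recorded fidelity scoring and feedback (sections 6.3 and 14) limit differences in delivery. Restricted randomisation (section 5.4.1) balanced site, facilitator and population characteristics; if those predict change, the simulations overstate the inflation.

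**The remedy has limits.** This also stands in part. Comparing facilitator means drops the site level and leaves the odds-ratio scale. Variation in change between the 5 sites was not simulated, so 12 df is untested in that case.

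**Conclusion.** The structural point holds. As written, the maternal interaction is tested against woman-level variation although facilitators are randomised. It keeps its 5% level only if change does not vary between facilitators or CP groups, and the plan neither states nor supports that condition.

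The size is conditional on assumed values. Type I error is about 5%, 8% and 11-12% at r = 0, 0.01 and 0.02 in both arms; about 6-7% and 8-9.5% at 0.01 and 0.02 if only the intervention arm varies; and about 5-6% on the plaque mapping. It would be wrong to conclude that the trial's error rate is inflated by a known amount. The change is worth making because it is cheap and removes an unstated assumption from a primary test. Confidence is medium.

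**What to change.** In section 12.4, state that the group-by-time contrast decides Primary Aim 1 and that the follow-up main effect is supportive. Give the contrast facilitator-level error in one of two ways:

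- **(a)** Average each woman's change (percentage of sites for BOP and PD4, score for plaque), or her baseline-adjusted follow-up value, by facilitator. Compare the 14 means with Welch's t-test.
- **(b)** Keep the GLMMs, and so the odds-ratio scale, and add facilitator-by-time and CP-group-by-time random effects, with 14 - 2 = 12 df.

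Then re-run the maternal power in section 12.2 under the chosen test, stating the contrast, the pre-post correlation and the variation in change that were assumed.

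**Cost.** No new data are needed, but there is a loss of precision. If change does not vary, the equal-variance form of (a) gives intervals about 10% wider, and 80% power under the planned test becomes about 72-73%. For Welch's version, a simulation with the same 8/6 layout (40,000 trials per point) gave about 13% wider and about 70%. Option (b) gives intervals about 20% wider and is conservative. If change does vary in both arms, power under the equal-variance t-test is about 63% at r = 0.01 and 55% at 0.02, for an effect that has 80% power when only woman-level variation is counted.
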